10.5 Participant Accrual and Retention

All women meeting criteria outlined in Section 5, including those identified as both pregnant and HIV-infected, will be recruited into this study. Once a participant has enrolled in the study, the study site will make every reasonable effort to retain her for the entire study period. A maximum of 5% loss-to-follow-up of enrolled pregnant women and infants will be targeted.

10.6 Data and Safety Monitoring Analysis

10.6.1 Interim Study Review (ISR) Committee

No Data and Safety Monitoring Board (DSMB) oversight is planned for this observational study, since pregnancy outcome data are assessed by the DSMB in their

review of the parent protocol. If treatment assignment is blinded in the parent protocol, the MTN ISR Committee will conduct interim reviews of study progress (pooled data only), including rates of participant accrual, retention, and assessment of the primary outcomes while the parent protocol is blinded. Additional reviews are anticipated to occur approximately annually following the initial review. At the time of these reviews, or at any other time, the protocol chair in combination with an external MTN reviewer may recommend that the study proceed as designed, proceed with design modifications, or be discontinued. The protocol chair or external MTN reviewer may consider recommending termination of this study if recruitment and retention are lower than targeted, or if study data quality is poor. The MTN-016 protocol leadership team will routinely monitor study conduct and progress (including participant accrual, retention and data quality); see the MTN-016 SSP for additional details. Once results from a parent protocol are unblinded and analyzed, analysis of the primary and secondary outcomes by study arm can be conducted.

10.7 Data Analysis

In most cases, the analyses will be stratified by parent protocol. However, when appropriate, analyses combining data from multiple protocols may be conducted. When the use of descriptive statistics to assess group or site characteristics or differences is required, the following methods will be used: for categorical variables, the number and percent in each category; for continuous variables, the mean, median, standard deviation, quartiles and range (minimum, maximum). Typically, within-arm assessment of the change from the baseline measurement to a follow-up measurement will be analyzed using McNemar's test (for categorical response variables) or the paired t-test or Wilcoxon signed-ranks test (for continuous variables). In general, when use of formal testing to assess differences between study arms is required, the following methods will be used: for binomial response variables, chi-square tests (or Fisher's exact test, if appropriate) and logistic regression; for continuous variables, t-tests and linear regression, or nonparametric methods if data are non-Normal. To assess baseline differences between study arms, participants will be compared for baseline characteristics including demographics and laboratory measurements using descriptive statistics.

The proportion of participants with adverse pregnancy and delivery outcomes (as specified in Section 10.2.1) will be compared by study arm using a Fisher exact test or chi-square test, depending on the prevalence, with a two-sided level of significance. The proportions of major malformations observed in infants will be compared using the same methods.

For each of the growth parameters (i.e., birth weight, serial length, weight, and head circumference), the mean observed in the active agent and non-active agent groups will be compared using a Student's *t*-test at selected time points: birth, one, six, and 12 months. More generally, GEE (generalized estimating equation) methods and robust variance estimates will be used to evaluate group differences over the first year. Incomplete data from infants that are lost to follow-up or terminate early in the study

(including from death) will be included in these analyses if a growth parameter is available at one of the selected time points.

Among infants who acquire HIV-1 infection, the proportion of infants with HIV-1 drug resistance mutations will be compared by study arm using Fisher's exact test with a two-sided level of significance.

Note that caution must be exercised in the interpretation of any difference (or lack of difference) found. Although characteristics of the women in the active arm and placebo/control arm should be similar at baseline (in the parent studies) due to randomization, women who become pregnant in the active agent group may not be similar to women who become pregnant in the non-active agent group (possibly due to a potential contraceptive effect of the active intervention).

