2.2 Background

While pregnancy is a common exclusion criterion in trials of candidate HIV prevention agents, it does occur among participants even when contraception is provided by the trial. Additionally, some trials (e.g., MTN-002, MTN-008) have been designed to evaluate the safety and pharmacokinetics of microbicide use at term and late preterm gestation. Thus, several opportunities exist to gather and analyze pregnancy

exposure data, which can inform safety profiles for candidate HIV prevention product use among reproductive age women. The need for data on exposures and infant outcomes of all candidate HIV prevention agents during pregnancy makes this registry an essential component of ongoing efforts to investigate the safety of these products. Since opening for enrollment, the MTN-016 study has collected data on exposure to drugs in pregnancy, potential confounding and/or relevant factors (such as maternal age, disease status during pregnancy, and gestational age at exposure, etc.), and pregnancy and infant outcomes. To date, the MTN-016 study has encountered no major obstacles to implementation. It is anticipated that new parent trials will open and operate under Version 2.0 of the MTN-016 protocol, e.g., excluding participants from MTN-003 (Vaginal and Oral Interventions to Control the Epidemic [VOICE]) and MTN-008.

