2.3 Study Hypotheses and Rationale

2.3.1 Study Hypotheses

We hypothesize the following:

- Exposures to prevention agents during pregnancy will not be associated with an increased risk of adverse pregnancy or delivery outcomes.
- Exposures to prevention agents during pregnancy will not be associated with an increased risk of major malformations among infants exposed *in utero*.

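### A two-sided test of difference is the only named primary analysis, and at the planned sizes its non-significance cannot support the hypothesis of no increased risk

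*Protocol*

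**What the plan says.** Protocol section 2.3.1 states the maternal hypothesis as "Exposures to prevention agents during pregnancy will not be associated with an increased risk of adverse pregnancy or delivery outcomes". A parallel hypothesis covers major malformations in infants exposed in utero. Neither carries a margin. The primary objectives in section 3.1 are worded as comparisons between active and placebo/control.

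Section 10.7 names the method for the maternal primary endpoints: the proportions "will be compared by study arm using a Fisher exact test or chi-square test, depending on the prevalence, with a two-sided level of significance". Malformations are compared by the same methods. No numeric significance level, effect measure or interval is given for either.

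The same section opens with "In most cases, the analyses will be stratified by parent protocol". It then adds "However, when appropriate, analyses combining data from multiple protocols may be conducted", without saying how the protocols would be combined. It closes by urging caution in reading either a difference or its absence, because "women who become pregnant in the active agent group may not be similar to women who become pregnant in the non-active agent group".

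Section 10.3 plans on 79 women and 68 infants per arm. It claims at least 80% power for an absolute difference of 16 points from 5% (maternal) and 13 points from 1% (malformations).

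**The concern.** The hypotheses claim an absence of harm, while the named analysis tests for any difference. If the test is significant for harm, the hypothesis is contradicted. If it is not significant, the plan yields nothing that bears on the hypothesis, because non-significance may mean no increase or too few events to see one. The registry exists to inform safety in pregnancy, so the non-significant case is the one where readers most need a number, and it is the case for which the plan names none.

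The closing caution in section 10.7 does not fill the gap. Its stated reason is selection into pregnancy, not lack of precision, and it offers no quantity by which an absence of difference could be judged.

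**Working it through.** **Inputs.** The sizes are 79 women and 68 infants per arm, with control rates of 5% and 1% and detectable differences of 16 and 13 points (section 10.3). The test is two-sided Fisher or chi-square (section 10.7). Significance level 0.05 is an assumption, since the text says only "with a two-sided level of significance". The alternatives of 10%, 15%, 3% and 5% below are illustrative.

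**Step 1: the plan's own figures.** Exact power is the sum, over all pairs of counts (x, y), of Bin(x; n, p₀)·Bin(y; n, p₁) for the tables with p ≤ 0.05.

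- Maternal, 5% vs 21%, n = 79: Fisher 83.0%, uncorrected chi-square 88%. The pooled-variance normal approximation gives 85.6%.
- Infant, 1% vs 14%, n = 68: Fisher 79.6%, uncorrected chi-square 90%. The normal approximation gives 82.8%.

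The stated figures therefore reproduce. For malformations, Fisher is a fraction of a point under 80%.

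**Step 2: the same calculation for smaller increases.**

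| True rates (control vs active) | n per arm | Fisher | Chi-square |
|---|---|---|---|
| 5% vs 10% | 79 | 14% | 23% |
| 5% vs 15% | 79 | 47% | 58% |
| 1% vs 3% | 68 | 1% | 8% |
| 1% vs 5% | 68 | 7% | 25% |

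A doubling of a 5% maternal risk would be missed 77% to 86% of the time. A tripling of a 1% malformation risk would be missed 92% to 99% of the time.

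**Step 3: what a perfectly null result would leave open.** The Newcombe interval combines the Wilson limits (l, u) of each arm. With equal proportions p, the half-width is √[(p − l)² + (u − p)²].

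- 4/79 in each arm: p = 0.0506, Wilson limits 0.0199 and 0.1231. Half-width = √(0.0308² + 0.0724²) = 0.079.
- 1/68 in each arm: p = 0.0147, Wilson limits 0.0026 and 0.0787. Half-width = √(0.0121² + 0.0640²) = 0.065.

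Identical counts thus remain compatible with an excess of up to about 7.9 points on a rate near 5%, and up to about 6.5 points on a rate near 1.5%.

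**Step 4: what the sizes could exclude.** The protocol gives no margin, so a range is shown. With equal true rates p, one-sided 0.025 and 80% power, n per arm = (1.96 + 0.84)²·2p(1 − p)/m².

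- p = 5%: m = 5 points needs 299 per arm, and m = 10 points needs 75.
- p = 1%: m = 2 points needs 389 per arm, and m = 5 points needs 63.

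Solved for m at the planned sizes, the smallest excludable excess is about 9.7 points for mothers and 4.8 points for infants. The infant figure is rough, because only about 0.7 events per arm are expected (68 × 0.01).

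**The case against.** The strongest defence is that the objectives only ask for a comparison, and a two-sided test makes one. Section 10.3 openly reports that only differences of 16 and 13 points are detectable, section 10.7 warns against over-reading a null result, and nothing forbids reporting intervals. This stands in part. Low sensitivity is disclosed, and the plan never says that non-significance will be called safety. But the hypotheses in section 2.3.1 go beyond a comparison, and the caution in section 10.7 rests on selection alone.

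A reader might also infer stronger faults that the protocol does not support:

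- **That the primary analysis is unstratified.** Section 10.7 stratifies by parent protocol in most cases. What remains is narrower: a plain Fisher or chi-square test is not itself a stratified test, so it would ignore parent protocol in the combined analyses that the section allows.
- **That section 10.7 admits a problem with pooling.** It permits combined analyses and concedes only selection into pregnancy. Section 10.3 expects essentially balanced arms, and if every combined trial were 1:1, differing baseline risks would not by themselves create a crude difference.
- **That the lack of covariate adjustment is an error.** Logistic regression is among the general methods, section 2.2 says data are collected on "potential confounding and/or relevant factors (such as maternal age, disease status during pregnancy, and gestational age at exposure, etc", and the choice of covariates commonly belongs in the analysis plan, which is not shown. Some obvious candidates are doubtful: HIV status may be affected by the assigned agent, and gestational age at enrolment is undefined for women enrolled after the outcome.
- **That two-sidedness is the fault.** The upper limit of a two-sided 95% interval serves well. What is missing is the interval.
- **That a null result is near certain under any real harm.** This fits small rises in malformations. For mothers, power is already 47% to 58% at 5% vs 15%.

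**Conclusion.** The point holds as a mismatch between hypothesis and analysis. Section 2.3.1 claims no increased risk, and section 10.7 names only a test of difference for both sets of primary endpoints. At the planned sizes that test has 14% to 23% power for a doubling from 5% and 1% to 8% for a tripling from 1%, so its non-significance cannot support the hypotheses. Identical counts would still leave about ±7.9 and ±6.5 points of uncertainty.

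These figures assume two-sided 0.05, equal arms of 79 and 68, no loss to follow-up and independent observations. The power figures also depend on the illustrative event rates. A numeric level stricter than 0.05, or losses, would lower power further. The detectable differences in section 10.3 are not in dispute. This is an improvement to the stated method, and it does not show that the trial would reach a wrong conclusion.

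**What to change.** In section 10.7, for each primary endpoint:

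1. Make the active-minus-control risk difference with a two-sided 95% confidence interval the primary result, by a method suited to sparse counts such as Newcombe or exact.
2. Keep the Fisher or chi-square p-value as secondary.
3. State that any conclusion on the section 2.3.1 hypotheses is limited to the largest excess that the upper limit excludes, and that non-significance alone does not establish them.
4. Keep the stratification by parent protocol. Where protocols are combined, use a stratified estimate (for example Mantel-Haenszel or exact stratified) in place of a crude two-by-two test.

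The cost is a few sentences of protocol text and some analysis code, with no new data or participants. The one downside is that wide intervals become visible to readers.

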7.5 Interim Visit: Mother

- Administrative
 - Locator information
 - Schedule next visit if indicated
- Clinical
 - Update medical history if indicated
 - Update medication history if indicated
 - Update pregnancy history if applicable

7.6 Newborn/Initial Visit:

If the pregnancy results or resulted in a live-born infant, a Newborn/Initial Visit for the infant should occur during the first ten days of life when possible. If local custom, medical status, or other reason deemed acceptable by the IoR/designee, prohibits a study visit during this time period, the infant's first visit may be delayed, or the visit may occur off-site, if possible. If the timing of the Newborn/Initial Visit corresponds to the visit window for a scheduled 1-, 6-, or 12-month follow-up visit, procedures need not be duplicated within that particular visit window.

Administrative

- Written informed consent for screening and enrollment of infant, or verbal confirmation of previous consent, if already obtained
- Eligibility assessment
- Identification number assignment (if not already assigned)
- Locator information
- Reimbursement
- Schedule next visit

Clinical

- Medical history
- Medication history
- Weight
- Length
- Head circumference
- Abdominal circumference (preferably within 10 days, but no later than Month 1 Visit)
- Physical exam
- Photographic documentation of suspected or confirmed anomalies as clinically indicated (to be sent to MTN Statistical Data Management Center (SDMC))

Laboratory

 If clinically indicated according to the loR/designee, US Food and Drug Administration (FDA)-approved HIV test with confirmatory tests as indicated

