7.7 Months 1, 6, and 12: Infant

The first visit for an infant may also occur after the first ten days of life in cases where the mother-infant pair is not yet enrolled, provided that this first visit for the infant occurs before the infant has reached their 1-year birth date. Day 0 for the infant is on the first day of life.

Months 1, 6, and 12

- Administrative
 - Locator information
 - Reimbursement
 - Schedule next visit (1 and 6 months only; if indicated for month 12)
- Clinical
 - Update medical history
 - Update medication history
 - Weight
 - Length
 - Head circumference
 - Physical exam (see Appendix III)
 - o If specific consent for this has been obtained, photographic documentation of suspected or confirmed anomalies as clinically indicated. Photographs should include at least the following images: Anterior-posterior (AP) and lateral of face/head, neck and upper third of thorax, standing up picture of child (front and back), hands, feet, as well as AP and lateral images of any suspected abnormal finding. Photographs should NOT be restricted to the suspected abnormal finding.
- Laboratory
 - As clinically indicated to follow a previous abnormal finding at the Newborn/Initial Visit

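### Infant growth is compared on raw means at nominal ages, with no account of actual age or sex and no stated source for the birth value

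*Protocol*

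**What the plan says.** Section 10.7 of the Protocol fixes the growth comparison: for each parameter, "the mean observed in the active agent and non-active agent groups will be compared using a Student's" t-test. The comparison is made at four nominal ages, listed as "selected time points: birth, one, six, and 12 months". It then adds that "GEE (generalized estimating equation) methods and robust variance estimates will be used to evaluate group differences over the first year". The growth paragraph names no standardised score, no covariate and no use of actual age. Earlier in the same section, the methods listed for continuous variables in general are "t-tests and linear regression, or nonparametric methods if data are non-Normal".

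The visit rules are flexible. Under Section 7.6, "a Newborn/Initial Visit for the infant should occur during the first ten days of life when possible", but for several reasons "the infant's first visit may be delayed". Section 7.7 adds: "The first visit for an infant may also occur after the first ten days of life", provided the infant is not yet one year old. Section 7.6 also foresees that this first visit may coincide with the 1-, 6- or 12-month window, in which case procedures need not be repeated. Section 7 leaves the windows themselves to the SSP Manual.

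Separately, the Pregnancy Outcome Visit in Section 7.4 collects infant sex, weight, length and head circumference, as available. Section 7.7 sets the infant's Day 0 at the first day of life.

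**The concern.** A t-test on observed means treats every measurement at a nominal visit as if it were taken at one age. Infants grow quickly, so part of the spread at a visit, and possibly part of the difference between arms, may reflect when the infant was measured. Sex adds further variation that could be removed, because it is already recorded.

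The birth time point is the least well defined. Two records could supply it: the delivery measurements of Section 7.4 and the Newborn/Initial Visit of Section 7.6, which aims at the first ten days and may be later. Section 10.7 names neither and sets no age limit. Leaving the choice open until the arms are unblinded invites a post hoc decision.

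Balance of age and sex between arms cannot be taken from randomization. Section 10.3 says that pregnant women are not randomized to arms, and the end of Section 10.7 warns that those who conceive may differ by arm.

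**Working it through.** The protocol gives no SD, effect size or power for growth, so there is no growth figure to reproduce. As a check on the inputs, the infant malformation example in Section 10.3 (68 per arm, 1% against 14%) was recomputed at two-sided 0.05. Power is 82.8% by the pooled normal approximation and 79.6% by exact Fisher, consistent with the stated 80%. The protocol gives no numerical significance level; 0.05 is assumed.

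**Inputs**
- From Section 10.3: 68 infants per arm.
- Assumed, not in the documents: SD of weight 500 g at a fixed age; constant early gain of 20-40 g/day; SD of age within a nominal visit of 3-21 days.

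**Detectable difference.** (1.96 + 0.84) × √(2/68) = 0.48 SD at 80% power, or about 240 g. With 65 per arm after 5% loss it is 0.49 SD.

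**Same age spread in both arms (precision only).** Total SD = √(500² + (gain × age SD)²). Power = Φ(240 / (total SD × √(2/68)) − 1.96). For example, at 30 g/day and an age SD of 7 days, total SD = √(250,000 + 210²) = 542 g and power is 73%.

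| Age SD (days) | Power at 20 g/day | Power at 30 g/day | Power at 40 g/day |
|---|---|---|---|
| 3 | 79% | 79% | 78% |
| 7 | 77% | 73% | 69% |
| 14 | 69% | 57% | 46% |
| 21 | 57% | 41% | 30% |

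**Different mean age by arm (bias).** Bias = gain × difference in mean age. Type I error is computed with SD 500 g and 68 per arm.
- 1 day: 20-40 g, type I error 5.6-7.5%.
- 3 days: 60-120 g, 11-29%.
- 5 days: 100-200 g, 22-65%. At 30 g/day this is 150 g, or 0.3 SD.

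**Sex.** Assume a 0.6 kg sex difference at 12 months, a within-sex SD of 1 kg and equal numbers of each sex. The added variance is (0.6/2)² = 0.09 against 1.0, or 9%. The SD rises by a factor of √1.09 = 1.044, which takes 80% power to about 76-77%.

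**Losses.** Bias = fraction lost × deficit of those lost. If 5% are lost in one arm only and are 0.5-1.5 SD smaller, the bias is 0.025-0.075 SD, against a detectable 0.48 SD. At 10% it is 0.05-0.15 SD.

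**The case against.** The strongest reply is that covariates, standardised scores and model details usually belong in the SAP, which is not at hand. Section 10.7 does allow linear regression for continuous variables, and GEE can carry age and sex terms. The late-visit permissions apply equally to both arms, and where the parent trial is blinded nothing in the protocol suggests that timing would differ by arm. The windows in the SSP Manual may be narrow.

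Much of this stands. It limits the expected harm to precision and leaves its size unknown. It does not remove the point, because the growth paragraph names a specific test on observed means, and that test cannot use age or sex. Blinding also follows each parent protocol (Section 10.4), so it is not assured throughout.

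Three stronger readings are tempting, but the documents do not support them.
- A reader might infer that late Newborn/Initial Visit values will be analysed as birth values. Nothing says so: delivery measurements are collected separately, and a late first visit can serve as the 1-, 6- or 12-month visit. The gap is only that the source is not named.
- A reader might infer that the GEE is unweighted and rests on a particular missingness assumption. The text is silent on both, and an SAP may settle them.
- A reader might see an error in the rule that data from infants who leave early, "including from death) will be included in these analyses if a growth parameter is available at one of the selected time points". Keeping real measurements from infants who later die is not an error. At the 5% loss target of Section 10.5 the dropout bias computed above is small. That target does not cover late entry, but nothing in the protocol shows that late entry depends on growth or differs by arm.

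**Conclusion.** The point holds as a weakness in the stated growth comparison. Raw means at nominal ages, without age or sex, are a poor match for visit rules this flexible, and the source of the birth value is undefined.

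With equal age spread and sex mix in the two arms, the consequence is lost precision: about 69-77% power in place of 80% at an age SD of 7 days, and little loss at 3 days. Bias arises only if timing or sex mix differs by arm. That is possible, because the compared groups are not randomized, but the protocol gives no sign of it.

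The growth figures rest on an assumed SD, daily gain and age spread. The weight-timing figures illustrate early weight only, and the documents offer no values for later visits, length or head circumference. Growth is a secondary endpoint, so the importance is modest.

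**What to change.** Amend the growth paragraph of Section 10.7, before arms are unblinded, as follows.

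- Compare growth using age- and sex-standardised z-scores computed at the actual age on the measurement date, or put actual age and sex as terms in the linear regression and GEE already planned.
- Take birth values from the delivery measurements in Section 7.4. Treat Newborn/Initial Visit values as measurements at their actual age.
- Report infant deaths by arm beside the growth results.
- Keep GEE. A likelihood-based mixed model would not resolve truncation by death, so replacing GEE is not clearly better.
- Show any gestational-age-corrected analysis as a sensitivity analysis only. Delivery before 37 weeks is itself a primary endpoint and may be an effect of exposure, so correcting for it could remove part of the effect of interest.

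The cost is wording and a standard score calculation; sex, visit dates and delivery measurements are already collected. There are two downsides: z-scores rely on a reference growth standard, and some birth values will be missing because delivery measurements are recorded only as available.
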